6.4.3 Late Delayed

Possible late delayed effects of radiotherapy include cataracts, and or eye damage leading to blindness, radiation necrosis, radiation leukoencephalopathy, radiation vasculopathy, pituitary dysfunction, radiation-induced neoplasms, and damage to the brainstem leading to significant motor or sensory deficits or even death.

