10.0 PATIENT ASSESSMENTS

10.1 Study Plan

- 10.1.1 Patients will receive concomitant temozolomide (75 mg/m² daily for 6 weeks) with radiotherapy as per standard of care.
- 10.1.2 Temozolomide will be taken orally prior to RT. The physician will discuss with the patient any eating restrictions, when other medications should be taken, and when temozolomide should be taken on the days without RT as per standard of care.
- 10.1.3 Adjuvant temozolomide 150-200 mg/m² D1-5 q28 days (+/- 5 days) for six cycles will be started approximately 4 weeks following completion of radiotherapy. Additional cycles may be continued at investigator's

- discretion. The first cycle will be prescribed at 150 mg/m², then increase to 200 mg/m² at cycle 2, toxicity permitting, as per standard of care.
- 10.1.4 Patients will receive RT at the University of Michigan or one of its affiliate centers. The patient will be considered eligible to receive concurrent and adjuvant chemotherapy through outside physicians closer to his/her home with continued follow-up at the University of Michigan per study guidelines

10.2 Study Specific Calendar	Pre-Ry		Prior to Each Chemotherapy Cycle	Follow-up Evaluation ^{a,g}					
			-			Mon	th		
				1	3	5	7	13	19
History & Physical Exam	X			Х	Х	X	X	X	Χ
KPS & Neurological Exam	х	x ^b (wk 6 of RT		x	х	x	X	X	X
QOL Evaluation/MDASI/MMSE ^c	х	x ^c (wk 6 of RT)		x	х	х	Х	X	Х
CBC w/ Diff, Platelets	Х	Xq	$\mathbf{X}_{\mathbf{q}}$						
Comprehensive metabolic panel	x		\mathbf{x}^{d}						
Neurocognitive evaluation	x b			x			Х		X
Gadolinium enhanced Brain MR ^e	Х			Х	Х	Х	х	Х	х
Advanced MRI	х	X ^f (wk 4 of RT)			x ^f				
11C MET PET	X ⁱ (optional)	X ^f (wk 4 of RT)							
Toxicity Notation	х	Х		Х	х	X	X	X	Х

- a) Timing of follow ups (1 month = 28 days): As per standard of care, patients will typically be seen in follow-up 1 month after completion of chemoradiation, then every 2 months +/- 2 week window. At the physician's discretion, after the first 6 months, follow-up visits may be approximately every 3 months. If a patient's temozolomide cycles are prolonged due to time for blood count recovery or other factors, assessments may be delayed in accord with the temozolomide cycles. At follow-up visits, history and physical exam, KPS and neurologic exam, and toxicity evaluations will be undertaken.
- b) KPS and recording of steroid and anticonvulsant dose will be required during week 6 of radiotherapy. NANO evaluation will be required at baseline

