11.0 STATISTICAL CONSIDERATIONS

This is a study of concurrent temozolomide and high dose radiation using biologic based target volume definition in patients with newly diagnosed glioblastoma (GBM).

The overall goal of this study is to determine if the treatment regimen described in this protocol is sufficiently promising to advance to a definitive randomized trial. Treatment for patients treated under this protocol will differ from standard care in the following ways:

- 1) High b-value diffusion-weighted and perfusion MRI will be used in target volume definition
- 2) The radiation dose to the boost volume will be 75 Gy based on earlier data demonstrating the safety and potential efficacy of this approach.
- **11.1** Primary objective: To improve overall survival at 12 months compared with published historical controls.

The final test addressing this aim will occur when the last enrolled patient completes 12 months of follow-up. If patients drop out or are lost to follow-up prior to 12 months, we will utilize the Kaplan-Meier approach to estimate OS at 12 months. Otherwise we will use the simple binomial proportion of patients who are alive within 12 months of treatment. We will test the null hypothesis that the true 12 months OS is equal to 0.65, based on recently reported survival rates from RTOG 0525 and RTOG 0825. The alternative hypothesis will be that 12 months OS is greater than 0.65. The test will be one-sided at an alpha=0.10 level. We will additionally use the Kaplan-Meier approach to estimated OS over time for all patients and according to MGMT and IDH1 status.

For example, MGMT status is an established prognostic factor in this setting with hazard ratios of approximately 2 for an endpoint of overall survival. On average we would expect a similar proportion of methylated patients in this trial as was observed for RTOG 0525 and RTOG 0825 (30%). However, with a sample size of 40, it is possible that the proportion of methylated patients will differ from 30% by a non-negligible amount. To account for this in the statistical analysis, we will weight patients so that the

weighted proportion of methylated patients is equal to 30%. Specifically, if p* denotes the observed proportion of methylated patients in this trial, the new weights will be .3/p* for methylated patients and (1-.3)/(1-p*) for unmethylated patients.

Sample size considerations:

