Patients will complete neurologic exam, mini mental status exam and EORTC global QOL questionnaire and specific brain module and MDASI-BT before, during and after treatment. The results will be summarized descriptively over time as well as by radiation dose. The relation between these outcomes and survival will be assessed by using QOL numbers as (possibly time dependent) predictors in a Cox regression model. Every effort will be made to avoid missing data. Missing data will be carefully considered as to whether it is missing at random or not. Mixed models with subject level random effects can provide valid estimation and inference under certain patterns of informative missingness and will be utilized where warranted. We will also perform simple checks whether for example subjects with decreased QOL are more likely to drop out. For example, we will compare observed QOL at time t amongst patients who did or did not drop out (i.e. decline to provide QOL data) by time t+1.

11.7 Interim analysis:

Due to a possible increased incidence of grade 3 or higher CNS toxicity (possibly, probably, or definitely related to treatment), we will analyze the data 6 months after the 20th patient completes radiation. At this point approximately 29 patients, out of the planned total of 40 patients eligible for radiation boost, will have been enrolled on the trial. It is possible that 6 patients will experience toxicity prior to this time point, in which case, the trial would be halted as soon as the 6th patient experiences toxicity. If the number of patients, out of the first 20, with toxicity (as defined above) is 6 or greater, the trial will be stopped due to possible safety concerns. The operating characteristics of this stopping rule are given in Table 1 below. When the true toxicity rate is 10%, just

1% of trials will stop early. On the other hand, if the probability of toxicity is 40%, 87% of trials will stop early. We note here that we do not expect to see excessive toxicity in this study because the volume of brain treated with the experimental (boost) dose of radiation will be limited to 1/3 the volume of brain, shown to be safe based on our prior dose-escalation study based on standard MRI alone.³⁰

Table 1. The proportion of trials stopping

True P(tox)	10%	20%	30%	40%
Proportion of	1%	20%	58%	87%
Trials				
Stopping				
Early				

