12.2 Data Safety and Monitoring

This trial will be monitored in accordance with the NCI approved University of Michigan Comprehensive Cancer Center Data and Safety Monitoring Plan.

The study specific Data and Safety Monitoring Committee (DSMC), consisting of the protocol investigators, data manager or designee, and other members of the study team involved with the conduct of the trial, will meet quarterly or more frequently depending on the activity of the protocol. The discussion will include matters related to the safety of study participants (SAE/UaP reporting), validity and integrity of the data, enrollment rate relative to expectations, characteristics of participants, retention of participants, adherence to the protocol (potential or real protocol deviations) and data completeness.

At the regular DSMC meetings, the protocol specific Data and Safety Monitoring Report form will be completed. The report will be signed by the Principal Investigator or by one of the co-investigators.

Data and Safety Monitoring Reports will be submitted to the University of Michigan Comprehensive Cancer Center Data and Safety Monitoring Board (DSMB) on a quarterly basis for independent review.

References:

- 1. M. R. Gilbert, M. Wang, K Aldape et al. RTOG 0525: A randomized phase III trial comparing standard adjuvant temozolomide (TMZ) with a dose-dense schedule in newly diagnosed glioblastoma (GBM), J Clin Oncol 29: #2006, 2011
- 3. Stupp, R., M. Hegi, et al. Effects of RT with concomitant and adjuvant temozolomide versus RT alone on survival in glioblastoma in a randomised phase III study: 5-year analysis of the EORTC-NCIC trial. Lancet oncology 10(5): 459-66, 2009.
- 4. Stupp, R., W.P. Mason, M.J. van den Bent, et al., Radiotherapy plus concomitant and adjuvant temozolomide for glioblastoma. N Engl J Med, 352(10): 987-96, 2005
- 6. M. Tanaka, Y. Ino and K. Nakagawa, *et al.* High-dose conformal radiotherapy for supratentorial malignant glioma: A historical comparison. *Lancet Oncol*, 6:953–960,2005

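### Section 11.7's only numerical toxicity rule ends at one look, with about 29 of 40 boosted patients enrolled; a scaled count that pauses accrual for review would be a cheap, modest addition

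*Combined protocol and SAP*

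**What the plan says.** Section 11.7 (Interim analysis) plans one look, 6 months after the 20th patient completes radiation. The rule is: "If the number of patients, out of the first 20, with toxicity (as defined above) is 6 or greater, the trial will be stopped". On timing it says: "At this point approximately 29 patients, out of the planned total of 40 patients eligible for radiation boost, will have been enrolled on the trial". If six patients have toxicity before the look, there is an earlier halt: "in which case, the trial would be halted as soon as the 6th patient experiences toxicity". Table 1 gives stopping proportions of 1%, 20%, 58% and 87% at true rates of 10%, 20%, 30% and 40%. No count is given for events after the look or for patients 21 to 40.

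General oversight continues under section 12.2. The study DSMC "will meet quarterly or more frequently depending on the activity of the protocol", and reports go to the cancer center's "Monitoring Board (DSMB) on a quarterly basis for independent review". Neither body is given a number to act on.

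Section 6.4.3 places necrosis among the late effects: "Possible late delayed effects of radiotherapy include cataracts, and or eye damage leading to blindness, radiation necrosis". The calendar in 10.2 runs toxicity notation to month 19, and its footnote a says: "At follow-up visits, history and physical exam, KPS and neurologic exam, and toxicity evaluations will be undertaken". Routine adverse-event collection under 12.1.1 closes 30 days after radiation.

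**The concern.** The plan judged 6 of 20 to be a rate worth stopping for. Once the look has passed, about 11 more patients (40 − 29) can be enrolled and treated to 75 Gy with no count in force, while late effects in earlier patients may still appear. A 6th event in the first 20 one week before the look halts the trial; one week after it, 11.7 prescribes nothing. At stake is how soon a high rate of serious CNS toxicity would prompt a formal review while patients are still being enrolled.

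**Working it through.** **1. Table 1.** Inputs from 11.7: n = 20, limit 6. P(X ≥ 6), X ~ Bin(20, p), is 0.0113, 0.1958, 0.5836 and 0.8744 at p = 0.1, 0.2, 0.3 and 0.4. This matches Table 1. A true 30% rate therefore passes the look with probability 1 − 0.5836 = 0.416, even if every event has occurred by then.

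**2. Carrying the count forward, all events counted.** Keep 6 of 20 and add 9 of 30 (the same 30% proportion):

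P = P(X₂₀ ≥ 6) + Σ P(X₂₀ = x) · P(Y₁₀ ≥ 9 − x), x = 0 to 5.

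At p = 0.3 the added terms are 0.1789 × 0.3504 = 0.0627 (x = 5), 0.1304 × 0.1503 = 0.0196 (x = 4), 0.0716 × 0.0473 = 0.0034 (x = 3) and 0.0003 for the rest, in total 0.0860. So P = 0.5836 + 0.0860 = 0.6696.

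| True rate | 10% | 20% | 30% | 40% |
|---|---|---|---|---|
| 6 of 20 only | 1.1% | 19.6% | 58.4% | 87.4% |
| 6 of 20, then 9 of 30 | 1.2% | 22.5% | 67.0% | 93.6% |

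The limit must scale with the denominator. Holding it at 6 up to 40 patients would trigger in 21% of trials at a 10% rate and 84% at 20%.

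**3. Accrual implied by the plan.** Nine patients (29 − 20) enrol between the 20th enrolment and the look. That interval is 6 months plus the time from enrolment to the end of radiation. With 0, 1.4 or 2.2 months for the latter (assumed), accrual is 9/6 = 1.5, 9/7.4 = 1.2 or 9/8.2 = 1.1 per month. The last 11 patients then take 11/1.5 = 7.3 to 11/1.1 = 10 months.

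**4. Follow-up at the look.** At 1.2 per month, patient k is 6 + (20 − k)/1.2 months past radiation. Months 13 and 19 (28-day months) are 12.0 and 17.5 calendar months. So 8 of the first 20 have not reached month 13 and 14 have not reached month 19. This is calendar time only; deaths lower the number actually evaluated.

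**5. Gain before accrual ends.** The documents give no onset time, so a range was simulated. Settings: 100,000 trials each, Poisson accrual of 1.2 per month, radiation ending 1.4 months after enrolment (mean 28.9 enrolled at the look), onset uniform from the end of radiation, only the first 20 counted before the look. True rate 30%; entries are for 6-month / 12-month onset.

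| Setting | Stopped by look | Further paused | Patients not enrolled, if each pause becomes closure |
|---|---|---|---|
| No competing death | 58.3% / 44.5% | 8.3% / 18.3% | 0.53 / 1.39 |
| Death, 12-month OS 0.82 | – | 7.6% / 15.2% | 0.48 / 1.16 |
| Death, 12-month OS 0.65 | 40.9% / 22.6% | 6.3% / 11.1% | 0.40 / 0.86 |
| Count checked quarterly, no death | – | 7.3% / 16.4% | 0.39 / 1.05 |
| Count checked quarterly, OS 0.65 | – | 5.6% / 10.0% | 0.30 / 0.65 |

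The 0.65 is the null value in 11.1 ("We will test the null hypothesis that the true 12 months OS is equal to 0.65"); 0.82 is the alternative for 40 patients. The death rows take 30% as the rate absent death; if 30% is already net of death, the no-death row applies. With 6-month onset the whole gain comes from 9 of 30; with 12-month onset about 13 of the 18 points come from a late 6th event in the first 20. Accrual of 1.1 or 1.5 per month gives 8.2% / 17.6% or 8.3% / 20.0% without death.

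**6. Cost when toxicity is acceptable.** Further pauses before accrual ends at a true 20% rate: 2.7% / 8.1% without death, 1.3% / 3.0% at OS 0.65. At 10%: at most about 0.6 point.

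**7. If the pre-look halt counts everyone enrolled.** At a 30% rate without death, the present rule then stops about 75% / 55% by the look, and the added gain falls to about 2% / 12% of trials.

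**The case against.** The strongest reply is that nothing here is wrong. The plan has a rule, a running halt and correct operating characteristics. Independent review continues every quarter, and nothing in 12.2 suggests that those bodies act only on a number. That stands, and it is why this is a refinement.

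The 30% rate lies exactly on the boundary and is not what the plan expects. The introduction reports no necrosis or late CNS toxicity at or below 75 Gy in the earlier dose-escalation study, and 11.7 expects no excess. At a 40% rate with 6-month onset and no death, the further gain is only about 6%, because the present rule already stops 87%. The larger 18% needs 12-month onset and no competing death. All of this stands.

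The column of patients not enrolled is an upper bound. It treats each pause as permanent closure and assumes that quarterly review would not otherwise have acted.

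A reader might infer stronger claims, which the documents do not support:
- *Safety is unmonitored after the look.* Section 12.2 says otherwise.
- *Late toxicity is not collected.* The 12.1.1 window closes early, but the 10.2 evaluations run to month 19.
- *The early-halt sentence should simply be limited to the first 20.* That sentence names no denominator. Table 1 implies the first 20: six among 29 would have probability 6.4% at a 10% rate, against the 1% shown. But if the sponsor means all enrolled patients, narrowing it would cut stopping by the look at a 30% rate from about 75% to 58%, or from 55% to 45%.

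**Conclusion.** The gap is real, and closing it is worth considering at low priority. No numerical trigger operates after the look, while about 11 patients remain to be enrolled over roughly 7 to 10 months. With all events counted, the added trigger gains 8.6 points at a true 30% rate (67.0 − 58.4) and 6.2 at 40% (93.6 − 87.4). These exact figures need no timing assumption. The gain while accrual is still open does: 8% or 18% of trials at a 30% rate, or 6% or 11% with death at OS 0.65, given the assumed uniform onset and the accrual inferred from the plan. The 0.3 to 1.4 patients spared per trial is a ceiling, not an expected benefit. All simulated gains take the pre-look halt to count only the first 20; under the wider reading they are smaller.

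**What to change.** 1. Add to 11.7: *After the look, and until accrual and radiation end, accrual is paused for DSMC and DSMB review if the cumulative number of boosted patients with qualifying toxicity reaches 6 among the first 20 boosted, including events after the look, or 9 among the first 30 boosted. Events are taken from the 10.2 toxicity evaluations.* Both denominators say boosted because 6.1 keeps patients with 1 cc or less of abnormality on study at 60 Gy.
2. Add a row to Table 1 for a stop or review with all events counted: about 1%, 23%, 67% and 94%. Note that the probability before accrual ends is lower.
3. Ask the sponsor whether the pre-look halt at the 6th event counts only the first 20 or all enrolled patients. If all enrolled, leave that scope as it is and make it explicit.

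A further limit of 12 of 40 is not worth adding: it raises the share paused before accrual ends by 0.3 point or less.

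Cost: one paragraph and one table row, with no new visit, committee or patient. The downside is extra pauses when toxicity is acceptable: at most about 0.6 point at a true 10% rate and 1 to 8 points at 20%. Each is a pause for review, not an automatic stop.

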Moreover, we evaluated the extent and severity of vascular leakage, as defined by gadolinium enhancement on MRI, as evidence of tumor aggressiveness in high grade glioma. We hypothesized that the vascular leakage volume pre-RT, reflecting disorganized angiogenesis typical of glioblastoma, would predict clinical outcome. We studied prospectively 20 patients with newly diagnosed high grade glioma. When time to progression was tested as a dependent variable, both the vascular leakage volume and vascular permeability were significant predictors.²⁹ In addition, early temporal changes during RT in heterogeneous regions of high and low perfusion in gliomas were found to predict response to RT.²⁹

These extensive studies demonstrate the prognostic importance of various parameters tested by MET PET and functional MRI, open the opportunity to select or combine the

best available imaging modalities to identify treatment-resistant tumor subvolumes that may benefit from locally intensified RT. As of yet, there is no published data looking at the value of interim MET PET or high b-value diffusion weighted imaging to evaluate early changes in tumor during chemoradiation that may potentially predict for outcome. The study we propose herein will also evaluate potential early changes in treatment as seen on MET PET and functional MRI, and correlate these changes with outcome.

Dose Escalation and Toxicity

An important aspect of tumor dose re-distribution and intensification is the need to keep toxicity at a level that does not exceed the level observed following standard therapy.

We have recently summarized our phase I-II TITE-CRM radiation dose-escalation study concurrent with temozolomide for GBM. IMRT doses were escalated from 66 to 81 Gy over 6 weeks and targets consisted of the entire contrast-enhancing lesion on MRI. Thirty-eight patients were analyzed with median follow-up of 54 months for patients who are alive. **No radiation necrosis or late CNS toxicity was observed at or below 75 Gy.** Median OS was an encouraging 20.1 months (95% CI: 13.2, 34.3). The probability of central field recurrence decreased with increasing dose (logistic regression, p<0.03). These findings showed that GBM patients can safely receive dose-escalated RT delivered with IMRT with concurrent temolozomide.³⁰

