3.0 PATIENT SELECTION

3.1 Eligibility Criteria

- 3.1.1 Newly diagnosed, histologically-confirmed supratentorial WHO grade IV gliomas including glioblastoma (all variants) and gliosarcoma.
- 3.1.2 Patients must be 18 years of age or older.
- 3.1.3 Karnofsky performance status ≥ 70
- 3.1.4 Minimal life expectancy of 12 weeks.
- 3.1.5 Adequate bone marrow reserve (Hemoglobin ≥ 10 g/dL, absolute neutrophils ≥ 1500/mm³, platelet count ≥ 100,000/mm³), acceptable liver function (total bilirubin ≤ 2 x upper limit of normal (ULN) (unless elevated bilirubin is related to Gilbert syndrome), and ALT/AST ≤ 5 x ULN) and renal function (serum creatinine ≤ 2.0 mg/dL) within 14 day prior to registration. Eligibility level for hemoglobin may be reached by transfusion.
- 3.1.6 Maximal contiguous volume of tumor based on high b-value diffusion MRI < 1/3 volume of brain
- 3.1.7 Patients must be registered within 6 weeks of most recent resection
- 3.1.8 Study-specific informed consent approved for this purpose by the IRB of the University of Michigan indicating that they are aware of the investigational nature of the treatment and the potential risks must be signed by the patient.

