6.0 RADIATION THERAPY

6.1 Radiation Dose and Fractionation

Radiation therapy will be delivered once daily for a total of 30 fractions, five days per week. If treatment is interrupted due to a non dose-limiting adverse event or any reason other than toxicity, including holidays, weather, transportation, or treatment machine problems, the duration of treatment will be extended accordingly. An initial treatment plan will be designed to simultaneously deliver differing doses per fraction to 2 PTV volumes: 60 Gy to the conventional MRI volume (PTV_Low), which is the volume and dose used in standard practice. An additional simultaneous boost will be delivered to the combination of high b-value diffusion and perfusion abnormality alone (PTV_High, the area assumed to be at highest risk of tumor recurrence).

Patients with a negative postoperative high b-value DW-MRI and perfusion MRI following complete resection will be treated to the post-operative resection cavity and conventional T1 MRI contrast-enhancing region to a total dose of 60 Gy, as per standard of care, and will remain on study to be analyzed with the entire study cohort. A negative high b-value DW-MRI or perfusion MRI will be defined as a combined high b-value DW-MRI and perfusion target volume of 1 cc or less. Radiation dose will be prescribed to ensure that at least 95% of the PTV (D_{95%}) should be covered by 100% of the prescription dose.

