6.2 Target Volumes

Target volumes will be based on the postoperative conventional MRI, and high b-value diffusion as well as perfusion MRI. Pre-operative conventional MRI should be reviewed in correlation with the post-operative residual tumor bed as per standard of care. Target volumes for this treatment are as follows:

Gross tumor volume, conventional MRI (GTV Low): shall be defined as the area of enhancement plus surgical cavity on pre-radiotherapy T1-gadolinium enhanced MRI, as per standard practice. If the conventional MRI does not show any abnormal enhancement, the GTV_Low will include the surgical cavity alone, as per standard practice.

Gross tumor volume, high b-value DW-MRI and perfusion MRI (GTV^HCV perf): shall be defined as the area of abnormality on pre-radiotherapy high b-value diffusion MRI and perfusion MRI. The HCV target volume will be defined as previously published 18 on b=3000 s/mm² diffusion weighted imaging by a threshold technique (mean intensity plus 2 standard deviations) calculated from a volume of interest in the normal-appearing brain tissue in the contralateral brain from the tumor.

Clinical target volume, conventional MRI (CTV Low): GTV_Low will be expanded by 1.7 cm to account for microscopic disease extension, and edited out of normal structures (e.g. calvarium, falx) as per standard of care.

Clinical target volume, high b-value DW-MRI and perfusion MRI (CTV^HCV perf): CTV^HCV will be set equal to the GTV^HCV

Planning target volume, conventional MRI (PTV Low): CTV_Low will be expanded by a margin of 0.3 cm, to account for daily patient set-up variability

Planning target volume, high b-value DW-MRI and perfusion MRI(PTV_High): CTV^HCV_perf will be expanded by a margin of 0.3-0.6 cm, or as appropriate to account for registration and daily patient set-up variability.

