6.3 Treatment Planning and Localization Requirements

Immobilization / Simulation: A treatment planning CT and/or MRI will be obtained with the patient in the same position and immobilization device as for treatment. All patients will be positioned and immobilized with individualized thermoplastic masks to ensure precise localization methods.

Treatment Planning: All patients will undergo MR-guided treatment planning with a high b-value diffusion MRI-defined boost volume. GTV definition, CTV definition, and PTV margin are as described above. CTV and relevant normal tissues will be outlined on planning scan slices. The PTV margins will ensure adequate dose coverage by correcting for variability in treatment set-up and registration variability. Intensity modulated radiotherapy (IMRT) or rapid arc plans will be used to achieve the highest prescription dose to the target, while minimizing dose to the normal brain and other critical structures. The tumor and critical organ constraints are described in further detail below.

Target Volume Coverage: PTV_Low will be treated with a prescription dose of 60 Gy in 2 Gy fractions over 30 fractions, with a minimum dose of 95% of the prescription dose. Additionally, the volume of PTV_Low receiving a dose > 105% of the boost PTV prescription dose will be minimized based on achieving the PTV Low dose prescription requirements.

PTV_High will be treated with a prescription dose of 75 Gy in 2.5 Gy fractions over 30 fractions. Minimum dose to PTV_High will be 95% of the prescription dose, and maximum dose should be no more than 105% of the prescribed dose (no plan that includes any dose greater than 110% will be accepted.)

Organs at Risk: The following critical normal tissues including the brain, brain stem, optic nerves, optic chiasm, and external surface will be outlined on the appropriate MRI/CT scans. Any compromises to the target because of physician decision to spare visual pathway or brainstem will be well-documented.

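### Section 11.7 says boost-dose brain is held to one third, but the only one-third rule (3.1.6) caps the contiguous diffusion volume, not the volume given 75 Gy

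*Combined protocol and SAP*

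**What the plan says.** Section 11.7 sets a stopping rule for grade 3 or higher CNS toxicity and then explains why excess toxicity is not expected: "the volume of brain treated with the experimental (boost) dose of radiation will be limited to 1/3 the volume of brain". It adds that this was "shown to be safe based on our prior dose-escalation study based on standard MRI alone". Section 1.0 says of that earlier study that "targets consisted of the entire contrast-enhancing lesion on MRI".

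One third of brain appears in only one other place, eligibility criterion 3.1.6: "Maximal contiguous volume of tumor based on high b-value diffusion MRI < 1/3 volume of brain".

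The boost itself is defined in section 6:

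- 6.1: "An additional simultaneous boost will be delivered to the combination of high b-value diffusion and perfusion abnormality alone".
- 6.2, boost GTV: "shall be defined as the area of abnormality on pre-radiotherapy high b-value diffusion MRI and perfusion MRI". The boost CTV is set equal to the GTV.
- 6.2, PTV_High: the boost CTV "will be expanded by a margin of 0.3-0.6 cm, or as appropriate", to allow for registration and set-up variability. The schema gives the same 0.3-0.6 cm without the open-ended words.
- 6.3: PTV_High is prescribed 75 Gy in 30 fractions. The treatment planning paragraph calls for "MR-guided treatment planning with a high b-value diffusion MRI-defined boost volume", which leaves out perfusion.

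Section 6.3 sets coverage and maximum-dose rules, asks planners to keep dose to normal brain low, and lists the brain among the structures to outline. It sets no limit on the size of PTV_High or on the amount of brain receiving the boost dose.

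**The concern.** Section 11.7 states a limit on irradiated brain. The rule that appears to stand behind it limits something else. The two volumes differ in three ways:

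- 3.1.6 counts diffusion abnormality only. The boost also covers perfusion abnormality.
- 3.1.6 counts the largest contiguous piece. The boost covers all of the abnormality.
- 3.1.6 is measured on the tumor before expansion. The boost dose goes to the tumor plus margin.

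Each difference makes the boosted volume equal to or larger than the volume that was screened. A patient can therefore pass 3.1.6 and have a plan that meets the rules in section 6 while more than one third of the brain lies within PTV_High.

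What is at stake is the safety rationale. Section 1.0 links the toxicity of earlier dose-escalation studies to high dose in large volumes of uninvolved brain, so boosted volume is a safety lever by the protocol's own reasoning. A reader of 11.7, including staff at the second center that is to treat 40 more patients identically, would believe that a planning limit is in place when section 6 contains none.

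**Working it through.** **The plan's own figures.** The only calculated figures in 11.7 are those in Table 1, the chance of stopping with 6 or more toxicities in 20 patients. The exact binomial P(X ≥ 6 | n = 20, p) gives:

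| True toxicity rate | Table 1 | Recomputed |
|---|---|---|
| 10% | 1% | 1.13% |
| 20% | 20% | 19.58% |
| 30% | 58% | 58.36% |
| 40% | 87% | 87.44% |

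Table 1 reproduces. The one-third limit is asserted without a derivation, so the question is whether it follows from 3.1.6.

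**Inputs.** The cap of one third of brain comes from 3.1.6 and the 0.3-0.6 cm margin from 6.2 and the schema. Brain volume and target shape are not in the documents. I assume 1200-1500 cc and a sphere.

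**Formulas.** Radius r = (3V/4π)^(1/3). PTV_High = (4/3)π(r + m)³ for margin m.

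**Step 1: a diffusion lesion at the 3.1.6 cap, with no perfusion volume.**

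| Brain | Cap | r | Margin | PTV_High | Share of brain | Over the cap |
|---|---|---|---|---|---|---|
| 1200 cc | 400 cc | 4.571 cm | 0.3 cm | 484.0 cc | 40.3% | 21.0% |
| 1200 cc | 400 cc | 4.571 cm | 0.6 cm | 579.1 cc | 48.3% | 44.8% |
| 1500 cc | 500 cc | 4.924 cm | 0.3 cm | 597.1 cc | 39.8% | 19.4% |
| 1500 cc | 500 cc | 4.924 cm | 0.6 cm | 706.0 cc | 47.1% | 41.2% |

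These shares are geometric PTV divided by brain volume. Margin that falls in skull or other non-brain tissue lowers them. A shape less compact than a sphere raises them.

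**Step 2: from PTV to boost dose.** Section 6.1 requires at least 95% of the PTV to receive the full prescription. In the smallest case above, 0.95 × 597.1 = 567.2 cc, and 567.2/1500 = 37.8%, still above one third.

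**Step 3: how large a target is needed.** Reversing the formula with (r − m), the combined target whose PTV_High just equals one third of brain is:

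| Brain | Margin 0.3 cm | Margin 0.6 cm |
|---|---|---|
| 1200 cc | 326.3 cc | 262.3 cc |
| 1500 cc | 414.1 cc | 338.6 cc |

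A breach therefore needs a combined target of roughly 260-410 cc or more.

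**Step 4: scale.** A 100 cc combined target has r = 2.879 cm and a PTV_High of 134.6 cc (0.3 cm) to 176.4 cc (0.6 cm). That is well inside a limit of 400-500 cc.

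**The case against.** The strongest reply is that 11.7 is itself part of the governing document and says that the volume will be limited. A plan above one third would contradict it. That stands. A reader might infer that the protocol makes no commitment at all, and the text does not support this. What is missing is the step in section 6 that would carry the commitment out.

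A second reply is that the margin is bounded. The schema gives 0.3-0.6 cm without qualification, and 6.2 ties the open-ended wording to registration and set-up. This also stands. A reader might infer a licence to enlarge the boost at will, but the stated purpose rules that out. The calculation uses only 0.3-0.6 cm.

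A third reply is that PTV is not brain, and part of a very large PTV would lie outside it. The percentages are therefore somewhat high for compact targets. The conclusion survives: a lesion at the cap already fills one third of brain. The limit would hold only if essentially the whole margin shell, 484.0 − 400 = 84.0 cc in the smallest case, fell outside the brain.

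A fourth reply is that 3.2.9 excludes multifocal disease. It does so for discontiguous contrast enhancement on conventional MRI. That may make large scattered targets less likely, but it limits neither diffusion nor perfusion volume.

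The word used in 6.1 for joining the two abnormalities could also be read as their overlap only. The boost would then be no larger than the diffusion volume and a breach would be rarer, but the margin would still be uncounted.

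Finally, the halt at the sixth toxicity and the quarterly safety review protect the cohort. They act after toxicity has occurred and do not check the individual plan.

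**Conclusion.** The point holds as a mismatch between a stated safety property and the rule meant to deliver it. Criterion 3.1.6 does not imply the 11.7 limit. With a spherical target and a 1200-1500 cc brain, the margin alone takes a lesion at the cap to a geometric PTV_High of about 40-48% of brain, less whatever margin lies outside the brain and before any perfusion volume is added. The difference between the two volumes is certain from the text. The percentages depend on the assumed brain size and shape.

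Three stronger readings are not supported:

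- A reader might infer that over-large boosts will be common. A breach needs a combined target of roughly 260-410 cc or more, and the documents give no distribution of volumes. It is likely rare, and its frequency cannot be stated.
- A reader might infer that the boost here is larger than in the earlier dose-escalation study. The imaging data in 1.0 come from a separate cohort and describe where the abnormalities lie relative to enhancement, not how large they are. Section 1.0 also states the aim of irradiating less brain.
- A reader might infer that the stopping rule is unsound. Table 1 reproduces, and neither it nor the power and primary analysis uses the one-third figure.

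**What to change.** Add a plan-acceptance check to 6.3: brain within PTV_High, meaning the combined diffusion and perfusion target with its margin, must be less than one third of contoured brain. If it is not, the boost volume is reduced, the change is documented, and the patient stays in the analysis. In the same section, correct the description of the boost volume to diffusion and perfusion MRI-defined, so that it agrees with 6.1 and 6.2.

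If the sponsor does not want the check, reword 11.7 to claim only what 3.1.6 caps: the largest contiguous diffusion volume at entry, before margin and without perfusion.

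The cost is one sentence and one wording correction in 6.3, or one reworded sentence in 11.7. Section 6.3 already requires the brain to be outlined and PTV_High is needed for planning, so no new data are required. The downside is that a rare patient with a very large target gets a smaller boost and still counts among those analyzed. Section 6.1 already keeps patients with no boost target in the cohort analysis, so this adds no new principle.
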